5.4 Criteria for Randomization and Initiation of Trial Treatment

Randomization should occur on Day 1 (Visit 2) after all Screening procedures have been completed; subject eligibility must be reviewed again and confirmed at the site on Day 1 prior to randomization. If a subject does not meet eligibility criteria, the subject can be retested and rescreened once at the Investigator's discretion as described in Section 7.1.1.

Eligible subjects will be randomized to treatment with M2951 (50 mg bid) or placebo through a central randomization process by an Interactive Web Response System (IWRS). This will be a double-blind trial. **CCI**

5.5

Criteria for Subject Withdrawal

Subjects will be informed they have the right to withdraw from the trial at any time, without prejudice to their medical care, and they are not obliged to state a reason for withdrawing. Any withdrawal must be fully documented in the electronic case report form (eCRF) and source documents, and should be followed up by the Investigator.

The Investigator may withdraw a subject at any time if this is considered to be in the subject's best interest.

5.5.1

Withdrawal from Trial Therapy

Subjects who withdraw from therapy must immediately return for an End of Treatment Visit followed by the Safety Follow-Up/End of Trial Visit 4 weeks later. A subject must be withdrawn from M2951 or placebo if any of the following occur:

- Adverse events, if discontinuation of IMP is desired or considered necessary by the Investigator and/or subject
- Use of prohibited medications, as defined in Section 6.5.2. However, any medications that are considered necessary for the subject's well-being may be given at the discretion of the Investigator.
- Pregnancy
- Protocol noncompliance judged as significant by the Investigator and/or the Sponsor
- Subject withdrew consent
- Subject lost to follow-up
- Lack of efficacy
- Death
- Participation in another investigational clinical trial.

Withdrawal due to special precautions are described in Section 6.5.4.

5.5.2

Withdrawal from the Trial

Subjects may withdraw from the trial at any time without giving a reason. Withdrawal of consent will be considered withdrawal from the trial. Subjects who withdraw from the trial while still on the IMP should return immediately for an End of Treatment Visit upon discontinuation of the IMP and a Safety Follow-Up Visit 4 weeks after the last administered dose of IMP. Subjects who

withdraw and are no longer on the IMP must complete the Safety Follow-Up/End of Trial Visit assessments described in Section 7.1.4.

A subject must be withdrawn if any of the following occurs during the trial:

- Pregnancy (for further details in case of pregnancy, see Section 7.4.2)
- Subject withdrew consent
- Participation in another investigational clinical trial
- Lost to follow-up
- Death
- Any events that endanger the safety of the subject.

If a subject fails to return for the post-treatment Safety Visit, all attempts should be made to contact the subject to ensure the reason for not returning is not an AE. Likewise, if a subject wishes to discontinue from the trial (eg, for personal reasons), an attempt should be made to establish the true reason is not an AE (bearing in mind the subject is not obliged to state the reasons).

If IMP is prematurely discontinued, the primary reason for discontinuation must be recorded in the appropriate section of the eCRF, and all efforts will be made to complete and report the observations as thoroughly as possible. A complete final evaluation at the time of the subject's withdrawal should be made and any AEs followed up until resolution or a period of 30 days after the last Safety Visit (or withdrawal from the trial).

If a subject has failed to attend scheduled trial assessments, the Investigator must determine the reasons and the circumstances as completely and accurately as possible.

Subjects who are withdrawn after randomization (eg, due to AEs or lack of efficacy) will not be replaced. Subjects who are withdrawn from the trial will not be allowed to re-enroll in the trial.

Participation in any other trial during the duration of this trial will not be allowed.

5.6 Premature Termination of the Trial

The clinical trial may be terminated prematurely or suspended at the request of Health Authorities or if new safety or efficacy information leads to an unfavorable risk benefit judgment for any IMP. The Sponsor may discontinue the trial if it becomes unjustifiable for medical or ethical reasons, for poor enrollment, or because of discontinuation of clinical development of an IMP or comparator from the market for safety reasons.

Health Authorities and Independent Ethics Committees (IECs)/Institutional Review Boards (IRBs) will be informed about the discontinuation of the trial in accordance with applicable regulations.

5.7 Definition of End of Trial

The end of the trial is defined as the last contact date with the last subject who participates in this trial (last subject's last visit).

A clinical trial protocol may not be considered closed as long as:

- Any subject is still receiving any IMP
- Visits specified by the protocol are still taking place
- Procedures or interventions according to the protocol are still being undertaken in any subject
- The post-treatment Follow-Up period, defined in the clinical trial protocol as being part of the trial, has not yet been completed for any subject.

6 Investigational Medicinal Product and Other Drugs Used in the Trial

The term IMP refers to an active substance or a placebo being tested or used as a reference therapy in a clinical trial, including products that have a marketing authorization but are formulated, packaged, or administered differently from the authorized form, used for an unauthorized indication, or used to gain further information about the authorized form.

6.1 Description of the Investigational Medicinal Product

During the 12-week treatment period, the active IMP is M2951 (2 x 25 mg bid), which is supplied as a capsule (size 0, color Swedish Orange) formulation for oral administration. No other excipients are used.

Identical capsules for placebo are filled with mannitol.

During the optional extension period, M2951 (2 x 25 mg bid) will be supplied as tablet formulation for oral administration.

The Sponsor, Merck KGaA, will provide IMP (M2951 and placebo) to the trial site, manufactured and tested according to applicable current Good Manufacturing Practice requirements for clinical trial supplies and a confirmation the IMPs are released for human use in clinical trials.

6.2 Dosage and Administration

During the 12-week treatment period, subjects will receive 50 mg bid M2951 or placebo administered as 2 matching oral capsules twice daily for 84 days. Subjects will self-administer the IMP at a set time each day (\pm 2 hours). Subjects must take their daily dose more than 1 hour prior to a meal or snack and more than 2 hours after a meal or snack. Clear fluids are allowed at any time. On trial visit days, the IMP will be administered during the trial visit after the scheduled trial visit procedures (other than post-treatment PK/PD sampling and post-treatment ECGs) are completed.

After completing the treatment period, subjects will be offered the opportunity to participate in an optional 6-month M2951 extension period on Day 85 (Visit 8). Subjects who received M2951 during the treatment period will continue with the same dose of M2951 (in tablet formulation). All subjects in the placebo group during the treatment period will discontinue placebo and start

treatment with 50 mg bid M2951 tablets on Day 85/Day 1 of OLE. On trial visit days, the IMP will be administered during the trial visit after the scheduled trial visit procedures are completed. Subjects will take 2 matching oral tablets twice daily for 6 months. Subjects will self-administer the IMP at a set time each day (\pm 2 hours). Subjects must take their daily dose more than 1 hour prior to a meal or snack and more than 2 hours after a meal or snack. Clear fluids are allowed at any time. On trial visit days, the IMP will be administered during the trial visit after the scheduled trial visit procedures are completed.

If a dose is missed, the subject can take the missed dose up to 6 hours after the scheduled time. If more than 6 hours have elapsed since the dose was missed, the subject should skip the dose for that period, make note of the missed dose, and take the next dose at the regularly scheduled time.

6.3 Assignment to Treatment Groups

Eligible subjects will be randomized through a central stratified randomization process by the IWRS to receive 50 mg bid M2951 or placebo in a 1:1 ratio prior to dosing on Visit 2/Day 1.

Treatment kits will contain enough medication for administration for 1 week (+ 2 days). In addition to the subject and Investigator/site, all Sponsor and CRO trial staff will be blinded to the treatment group assignment.

Subjects continuing to the open-label extension period will be dispensed additional treatment kits for 6 months of treatment.

6.4 Noninvestigational Medicinal Products to be Used

Throughout the study, patients will remain on their chronic stable doses of MTX at the time of Screening (refer to Section 5.3.1) as part of their standard of care and adjusted only for safety reasons.

6.5 Concomitant Medications and Therapies

All concomitant medications taken by the subject during the trial from the date of signature of informed consent (including those participating in and during the extension period) are to be recorded in the appropriate section of the eCRF, noting the name, dose, duration, and indication of each drug. Nondrug interventions and any changes to a concomitant medication or other intervention should also be recorded in the eCRF.

6.5.1 Permitted Medicines

Permitted medications are any medications required per the medical history and not specifically prohibited by the protocol during the trial. These standard of care medications are part of the subject's previous RA treatment and will therefore not be provided by the Sponsor. Any such medications prescribed or used should be recorded in the eCRF.

The standard of care therapies for RA that are allowed to be continued during the trial include the following immunosuppressive or immunomodulating therapies:

- MTX (up to 25 mg/week) background therapy is required
- Sulfasalazine (up to 3 g/day)
- Oral corticosteroids (up to 10 mg/day prednisone equivalent)

Other permitted therapies that are allowed to be continued during the trial include antimalarials, such as hydroxychloroquine, quinacrine, and chloroquine.

With the exception of corticosteroids, the dose of which can be decreased, the dose of these medications must remain stable during the Screening Period and throughout the subject's participation in the trial, unless changes are required for safety issues.

The following additional treatments commonly given to subjects with RA are permitted to be continued during the trial and should be maintained at a stable dose during the trial unless a dose change is required for safety reasons:

- Nonsteroidal anti-inflammatory medications
- Opioids and other analgesics.

Any medications (other than those excluded as per exclusion criteria in Section 5.3.2 or prohibited as per Section 6.5.2) that are considered necessary for the subjects' welfare and will not interfere with the trial medication may be given at the Investigator's discretion.

6.5.2 Prohibited Medicines

The following medications and therapies are not permitted during the trial and would require discontinuation of the trial treatment:

- Initiation of an immunosuppressant or immunomodulator, or increase in immunosuppressant beyond the maximum allowable dose
- Oral corticosteroid dose > 10 mg/day or use of intramuscular or intravenous steroids
- Intra-articular steroids
- Biologic therapies
- Intravenous Ig therapy and/or plasmapheresis
- Live and live-attenuated vaccines
- Herbal supplements including, but not limited to, St. John's wort, grapefruit, Seville oranges, cranberries, or juices of these fruits
- Moderate or strong inhibitors or inducers of CYP3A or drugs mainly metabolized by CYP3A with a narrow therapeutic index (see Table 2). The additive effects of weak inhibitors taken in combination must also be taken into account.

New therapies for RA should not be initiated during the trial. Initiation of any new immunosuppressant or immunomodulatory therapy would be considered a treatment failure and should result in withdrawal of the subject from the IMP (see Section 5.5.1).

Table 2

Examples of Inhibitors or Inducers of CYP3A Enzymes or Substrates with Narrow Therapeutic Range

Inhibitors		
Strong	Moderate	Weak
Boceprevir, clarithromycin, conivaptan, grapefruit juice, ^a indinavir, itraconazole, ketoconazole, lopinavir/ritonavir, mibefradil, nefazodone, neflifinavir, posaconazole, ritonavir, saquinavir, telaprevir, telithromycin, voriconazole	Amprenavir, aprepitant, atazanavir, ciprofloxacin, darunavir/ritonavir, diltiazem, erythromycin, fluconazole, fosamprenavir, grapefruit juice, ^a matinib, verapamil	Alprazolam, amiodarone, amlodipine, atorvastatin, bicalutamide, cilostazol, cimetidine, cyclosporine, fluoxetine, fluvoxamine, ginkgo, goldenseal, soniazid, nilotinib, oral contraceptives, ranitidine, ranolazine, tipranavir/ritonavir, zileuton
Inducers		
Strong	Moderate	Weak
Avasimibe, carbamazepine, phenytoin, rifampin, St. John's wort	Bosentan, efavirenz, etravirine, modafinil, naftilin	Amprenavir, aprepitant, armodafinil, echinacea, pioglitazone, prednisone, rufinamide
Substrates With a Narrow Therapeutic Range		
Alfentanil, astemizole, ^b cisapride, ^b cyclosporine, dihydroergotamine, ergotamine, fentanyl, pimozide, quinidine, sirolimus, tacrolimus, terfenadine ^b		

^a The effect of grapefruit juice varies widely among brands and is concentration, dose, and preparation dependent. Studies have shown that it can be classified as a "strong CYP3A inhibitor" when a certain preparation is used (eg, high dose, double strength) or as a "moderate CYP3A inhibitor" when another preparation is used (eg, low dose, single strength).

^b Withdrawn from the US and certain other markets because of safety reasons.

Note: This is not an exhaustive list. For an updated list, see Tables 5, 6, and 7 in the following link: <http://www.fda.gov/Drugs/DevelopmentApprovalProcess/DevelopmentResources/DrugInteractionsLabeling/ucm080499.htm>

Note: A strong inhibitor is defined as an inhibitor that increases the AUC of a substrate sensitive for that CYP \geq 5-fold or decreases clearance by $> 80\%$, and a strong inducer decreases AUC of a substrate by $\geq 80\%$.

Note: A moderate inhibitor is defined as an inhibitor that increases the AUC of a substrate sensitive for that CYP ≥ 2 -fold but < 5 -fold or decreases clearance by 50%-80%, and a strong inducer decreases AUC by 50%-80%.

Note: A weak inhibitor is defined as an inhibitor that increases the AUC of a sensitive substrate for that CYP < 2 -fold or decreases clearance 20%-50%, and a weak inducer decreases AUC by 20%-50%.

Note: CYP substrates with narrow therapeutic range refers to drugs whose exposure-response relationship indicates that small increases in their exposure levels by the concomitant use of CYP inhibitors may lead to serious safety concerns (eg, Torsades de pointes).

6.5.3 Other Interventions

Not applicable.

6.5.4 Special Precautions

The IMP should be temporarily withheld or permanently withdrawn if the following abnormalities occur or re-occur, as relevant, and only 1 re-initiation is allowed if the IMP is temporarily withheld:

- For a neutrophil count $< 500/\text{mm}^3$ or platelet count $< 25,000/\text{mm}^3$ (Grade 4) or neutrophil count 500 to 999/mm³ (Grade 3) with fever or platelet count 25,000 to 49,999/mm³ (Grade 3) with bleeding, the IMP should be permanently withdrawn.

- For a Grade 3 decrease in neutrophil count without fever or Grade 3 decrease in platelet count without bleeding, temporarily hold the IMP and recheck the value within 24 hours of receipt. If the value is still Grade 3, permanently discontinue the IMP. For a decrease from normal to Grade 1, or Grade 1 to Grade 2, temporarily hold the IMP and recheck the value within 24 hours of receipt. Discontinue the IMP if the neutrophil or platelet count continues to decrease, and re-initiate the IMP if no downward trend is observed.
- For an increase in AST or ALT to $> 3X$ ULN or increase in bilirubin to $> 1.5X$ ULN (Grade 2 or higher), the IMP should be permanently withdrawn.
- For an increase in amylase or lipase to $> 5X$ ULN (Grade 4), the IMP should be permanently withdrawn.
 - For an increase in amylase or lipase to > 2 to $5X$ ULN (Grade 3), temporarily hold the IMP and recheck the value within 24 hours of receipt. If the value is still Grade 3, permanently discontinue the IMP. For any other increase from Baseline to another grade, temporarily hold the IMP and recheck the value within 24 hours of receipt. Discontinue the IMP if the value does not decrease, or re-initiate the IMP if a downward trend is observed.
- For an increase in serum creatinine to $> 3X$ from Baseline (Grade 3 or higher), the IMP should be permanently withdrawn.
 - For any other increase in serum creatinine $> 1.5X$ from Baseline, temporarily hold the IMP and recheck the value within 24 hours of receipt. Discontinue the IMP if the value does not decrease, or re-initiate the IMP if a downward trend is observed.
- For any other laboratory abnormality of Grade 4 severity, the IMP should be permanently withdrawn.
 - For any other laboratory increase/decrease (as relevant) from Baseline to a higher severity grade, temporarily hold the IMP and recheck the value within 24 hours of receipt. Discontinue the IMP if the value does not improve, or re-initiate the IMP if an improving trend is observed.

Duplicate blood samples will be collected for selected safety laboratories to be processed by both the central laboratory and local laboratories. A detailed list of these tests is provided in the Laboratory Manual. The Investigator should review local laboratory results within 24 hours and should base decisions regarding retesting or IMP dose interruption or discontinuation on local laboratory results if local laboratory results are obtained prior to the central laboratory results and show an abnormality requiring action. The local laboratory reference range should be used to determine grade in this case. Only the central laboratory results will be automatically reported and used for analyses. If an action is taken to retest or adjust the IMP dose based on local laboratory results, the results should be entered in the eCRF (with date, time and result, and local reference range) on an unscheduled visit page to document why the decision was made.

Laboratory values corresponding to Common Terminology Criteria for AEs (CTCAE) Grades 1 to 4 are presented for selected laboratory parameters in [Table 3](#). For all other laboratory abnormalities, refer to the CTCAE, version 4.03 ([20](#)).

Table 3 CTCAE Grades for Relevant Laboratory Parameters

Laboratory Parameter	Grade 1	Grade 2	Grade 3	Grade 4
Neutrophil (/mm ³)	< LLN to 1,500	< 1,500 to 1,000	< 1,000 to 500	< 500
Platelets (/mm ³)	< LLN to 75,000	< 75,000 to 50,000	< 50,000 to 25,000	< 25,000
AST and ALT	< ULN to 3X ULN	> 3 to 5X ULN	> 5 to 20X ULN	> 20X ULN
Bilirubin	< ULN to 1.5X ULN	> 1.5 to 3X ULN	> 3 to 10X ULN	> 10X ULN
Amylase and lipase	< ULN to 1.5X ULN	> 1.5 to 2X ULN	> 2 to 5X ULN	> 5X ULN
Creatinine	> Baseline to ≤ 1.5X Baseline, or > ULN to 1.5X ULN	> 1.5 to 3X Baseline or > 1.5 to 3X ULN	> 3X Baseline, or > 3 to 6X ULN	> 6X ULN

ALT=alanine aminotransferase, AST=aspartate aminotransferase, CTCAE=Common Terminology Criteria for Adverse Events, LLN=lower limit of normal, ULN=upper limit of normal.

The reason for IMP withdrawal and the nature, duration, and results of any planned follow-up observations should be recorded in the appropriate section of the eCRF.

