10. History of or current diagnosis of active tuberculosis (TB); undergoing treatment for latent TB infection (LTBI); untreated LTBI (as determined by documented results within 3 months of the Screening Visit of a positive TB skin test with purified protein derivative with induration ≥ 5 mm, a positive QuantiFERON®-TB test or positive or borderline T-SPOT [Elispot] test); or positive QuantiFERON-TB test at Screening. Subjects with documented completed appropriate LTBI treatment would not be excluded and are not required to be tested.
 - Subjects with current household contacts with active TB will also be excluded.

- Indeterminate QuantiFERON-TB or T-SPOT tests may be repeated once, and will be considered positive if retest results are positive or indeterminate.

11. History of splenectomy at any time, or any major surgery within 2 months prior to Screening
12. History of myocardial infarction or cerebrovascular event within 6 months prior to Screening, or current active angina pectoris, symptomatic heart failure, uncontrolled seizures, untreated hypertension, GI bleeding, or any other significant active medical condition in the Investigator's opinion
13. On anticoagulation or antiplatelet therapy other than daily aspirin for cardioprotection
14. On fish oil (unless discontinued prior to first dose)
15. History of cancer, except adequately treated basal cell or squamous cell carcinoma of the skin (no more than 3 lesions requiring treatment in lifetime) or carcinoma in situ/cervical intraepithelial neoplasia of the uterine cervix, unless considered cured > 5 years
16. Breastfeeding/lactating or pregnant women
17. Clinically significant abnormality on ECG, or an active infective process or any other clinically significant abnormality on Screening chest X-ray (CXR) taken within 4 weeks of the first dose, per Investigator opinion. If a CXR has been taken within the previous 3 months and results are available and normal, the CXR does not need to be carried out
18. Estimated glomerular filtration rate by the 4-variable Modification of Diet in Renal Disease equation (19) of < 45 mL/min/1.73 m²
19. TSH < 0.01 or ≥ 7.1 mIU/L at Screening
20. Alanine aminotransferase (ALT), aspartate aminotransferase (AST), amylase, or lipase > 2X above upper limit of normal (ULN) of laboratory reference range, total bilirubin > 1.5X ULN, any other clinically significant laboratory abnormality
21. B cell (CD19) count < 50% of the lower limit of normal at Screening

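### The creatinine stop in Protocol Section 6.5.4 is labelled Grade 3 or higher but uses only one of Table 3's two Grade 3 limits, so its text conflicts when Baseline is above ULN

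*Protocol*

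**What the plan says.** Section 6.5.4 of the Protocol has two creatinine rules.

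- **Permanent stop.** The trigger is a rise to > 3X "from Baseline (Grade 3 or higher), the IMP should be permanently withdrawn".
- **Hold.** The sub-bullet begins "For any other increase in serum creatinine" and covers rises > 1.5X Baseline. The IMP is held and the test repeated within 24 hours of the result. The instruction is then: "Discontinue the IMP if the value does not decrease, or re-initiate the IMP if a downward trend is observed". No grade or level is attached to the restart.

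The section opens with a limit on all holds: "only 1 re-initiation is allowed if the IMP is temporarily withheld".

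Table 3 in the same section gives Grade 3 creatinine two arms: "> 3X Baseline, or > 3 to 6X ULN".

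For neutrophils and platelets (uncomplicated Grade 3) and for amylase and lipase, Section 6.5.4 states what follows a repeat test that has not improved in grade: "If the value is still Grade 3, permanently discontinue the IMP". The creatinine rules have no such line.

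Section 5.3.2 limits renal function at entry in two ways. Exclusion 18 uses "Estimated glomerular filtration rate by the 4-variable Modification of Diet in Renal Disease equation", with a cut-off of 45 mL/min/1.73 m². Exclusion 20 ends with "any other clinically significant laboratory abnormality". Neither states a creatinine limit as a multiple of ULN.

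**The concern.** The stop bullet presents its number as equivalent to a grade, but the number matches only the Baseline arm of that grade. For a subject who enters with creatinine above ULN, there are values that Table 3 calls Grade 3 and the number does not reach. Two instructions then compete: the label says stop for good, and the sub-bullet for all other rises says hold, repeat, and restart if the value is falling.

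What is at stake is consistent handling of a raised creatinine across roughly 50 sites. Renal toxicity is among the important potential risks in Section 3.1, and the subjects concerned are those who start with raised creatinine.

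**Working it through.** No sample-size or error-rate figure is involved. The check is whether the stop number and the Grade 3 definition pick out the same values.

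**Inputs**
- Stop: above 3X Baseline (Section 6.5.4).
- Hold: any other rise above 1.5X Baseline (Section 6.5.4).
- Grade 3: above 3X Baseline, or above 3 to 6X ULN (Table 3). Grade 4: above 6X ULN.
- Baseline creatinine b, in multiples of ULN. The documents give neither ULN nor Baseline creatinine, so b is an assumption, shown from 1.0 to 1.4.

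**Formulas, in multiples of ULN**
- The stop starts above 3b.
- Grade 3 or higher starts above the smaller of 3b and 3.
- The hold starts above 1.5b.

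**Baseline at or below ULN (b ≤ 1).** Then 3b ≤ 3, so Grade 3 starts at 3b, exactly where the stop starts. The label is correct and there is no gap.

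**Baseline above ULN (b > 1).** Then Grade 3 starts at 3 but the stop starts at 3b. Values above 3 and up to 3b are Grade 3 without meeting the number.

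| b (assumed) | Stop above (3b) | Grade 3 but below the stop | Hold above (1.5b) | 3X ULN as a multiple of Baseline (3/b) |
|---|---|---|---|---|
| 1.0 | 3.0 | none | 1.50 | 3.00 |
| 1.1 | 3.3 | over 3 to 3.3 | 1.65 | 2.73 |
| 1.2 | 3.6 | over 3 to 3.6 | 1.80 | 2.50 |
| 1.3 | 3.9 | over 3 to 3.9 | 1.95 | 2.31 |
| 1.4 | 4.2 | over 3 to 4.2 | 2.10 | 2.14 |

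The hold threshold is at or below 3 whenever b ≤ 2 (1.5 × 2 = 3), so every gap value in the table falls under the hold sub-bullet. The rule on other laboratory abnormalities of Grade 4 does not help, because these values are Grade 3.

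**Example, b = 1.2.** A value of 3.5X ULN is 3.5/1.2 = 2.92X Baseline: Grade 3, below the number, above the hold threshold. A repeat of 3.2X ULN is 3.2/1.2 = 2.67X Baseline. That is a fall of (3.5 − 3.2)/3.5 = 8.6%, and the value is still Grade 3. Read by its numbers, the text allows a restart if the site regards this as a downward trend, a term the section does not define. Read by its label, the IMP should have been stopped at the first value.

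**After the fix.** With a stop at above 3X Baseline or above 3X ULN, the stop starts at the smaller of 3b and 3. That is the Grade 3 threshold at every b, and the gap is empty.

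**The case against.** **The label already covers it.** A site that grades 3.5X ULN gets Grade 3 and finds a bullet marked Grade 3 or higher that orders a permanent stop. This stands to the extent that the text does not clearly permit a restart. It does not remove the conflict, because the number is a multiple of Baseline and the sub-bullet takes in all other rises.

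**A Baseline-relative trigger is a legitimate choice.** In someone who starts high, change from their own level is a sensible measure of drug effect, and the fix would stop such subjects at less than 3X their Baseline. That is a fair description of the cost. But the sponsor has labelled the trigger with a grade, and that grade has a ULN arm.

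**Other safeguards exist.** Section 5.5 lets the investigator withdraw a subject at any time. Section 5.5.1 requires withdrawal from the IMP for an adverse event when stopping is judged necessary, and Section 5.5.2 requires withdrawal from the trial for events that endanger safety. An IDMC reviews safety data. All of this limits the harm. None of it settles which creatinine rule applies, since each provision depends on judgement.

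**The comparison with other laboratory tests is selective.** Thresholds in Section 6.5.4 differ by test. Above 3X Baseline, creatinine stops at once, whereas uncomplicated Grade 3 neutrophils, platelets, amylase and lipase first get a hold and a repeat. A reader might infer that the creatinine rule is generally laxer. It is not: the difference in the lax direction arises only when Baseline exceeds ULN.

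**The SAP replaces Table 3.** SAP Section 9 sets Table 3 aside for grading, but it calls only Grade 1 entries wrong, and it governs analysis. It does not amend the dosing rule at sites.

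**Conclusion.** The conflict is real and narrow. It rests on one condition, a Baseline above ULN, which the entry criteria do not bar as such. In that case a Grade 3 value can meet the label of the stop bullet and the number of the hold sub-bullet together.

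Two stronger readings are tempting. The first is that the Protocol plainly authorises a restart at Grade 3; the label in the stop bullet makes the text contradictory rather than permissive. The second is that a stated share of the 64 subjects is at risk. The documents do not give the number with Baseline above ULN, and exposure would also require a rise above 3X ULN that stays within 3X Baseline, a fall on repeat that remains above 3X ULN, an unused restart, and a decision to restart. The widths in the table are ranges of laboratory values under assumed Baselines, not frequencies of events.

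The IMP is held and creatinine repeated in any case, and only one restart is possible. No endpoint, analysis set or error rate changes. This is a minor safety-wording correction.

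**What to change.** In the creatinine bullet of Section 6.5.4, change the trigger to read *to > 3X Baseline or > 3X ULN (Grade 3 or higher)* and leave the permanent-withdrawal instruction and the hold sub-bullet as they are. Section 6.5.4 already says when the local laboratory's reference range decides the grade, so no further rule on ULN is needed.

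The cost is one wording change by amendment and a notice to sites. It needs no new data or visits and does not touch blinding or analysis. The downside is possibly a few extra permanent stops, only in subjects whose Baseline is above ULN and at less than 3X their own Baseline (for assumed Baselines of 1.1 to 1.4X ULN, at 2.73X down to 2.14X).
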